5.6.4 Planning Priorities

The priorities in addressing the protocol aims and constraints will be in the following order:

- 1) Group 1 (table 6),
- 2) Group 2 (table 6),
- 3) Group 3 (table 6).

5.8 External Beam Equipment and Beam Delivery Methods

Megavoltage equipment capable of delivering static or dynamic intensity modulation with a multileaf collimator is used. Whole field IMRT (without an anterior AP field) is used.

5.9 Treatment Verification and daily imaging

- Pre-treatment radiation therapy planning CT scan;
- Daily imaging with cone beam CT (5.1.5.1)

5.10 Quality Assurance of Target Volumes and Critical Structure Volumes

The DVH's of each target and Oar will be exported and converted to excel file format.

5.10.1 Each treatment shall be scored with regard to the coverage of each PTV (*i.e.* *PTV70*, *PTV63*, *PTV58.1*, and *PTV50.75*) and with regard to the level of sparing of several OAR's; the scores to be assigned are defined in table 8 below.

Table 8.

	Per protocol	Minor variation	Major variation
Overall treatment time	47 days	48-51 days	>51 days
PTV coverage	V95%>99%	95%<V95%<99%	V95%<95%
Cord + 4 mm	Max Dose 45Gy	Max Dose 47.5Gy	Max Dose 49.5Gy
Brainstem	Max Dose 54Gy	Max Dose 56.7Gy	Max Dose ≤ 59.4Gy
Brain	Max Dose 60Gy	Max Dose 63Gy	Max Dose 66Gy
Larynx for edema	V50 < 30%	30% < V50 < 31.5%	31.5% < V50 < 33%
Mandible	Max Dose 70Gy	Max Dose 73.5Gy	Max Dose 75Gy
Superior constrictor	V40 < 95%	95% < V40 < 100%	
Superior constrictor	V50 < 90%	90% < V50 < 94.5%	94.5% V50 < 99%
Superior constrictor	V60 < 80%	80% < V60 < 84%	84% < V60 < 88%
Superior constrictor	V65 < 70%	70% < V65 < 73.5%	73.5% < V65 < 77%
Parotids	V30 < 50%	50% < V30 < 52.5%	52.5% < V30 < 55%
Esophagus	Max Dose 45Gy	Max Dose 47.3Gy	Max Dose 49.5Gy
Brachial plexus	Max Dose 60Gy	Max Dose 63Gy	Max Dose 66Gy
Inner Ears	Mean Dose 40Gy	Mean Dose 42.5Gy	Mean Dose 45Gy

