5.5 PTV and subPTV generation

Each CTV is expanded 5 mm isotropically to generate corresponding PTV's, PTV1, 2 and 3. Each PTV is further adjusted to come off the skin, by excluding the part that is within 3 mm to skin surface (PTV= CTV + 5mm – (skin -3mm)).

In order to achieve dose de-escalation on parts of the PTV (subPTV), each PTV is further divided into subPTV's whose prescription dose is as follows in table 6.

Table 6

Main PTV	SubPTV	Note	Px D (Gy)	Nomenclature
PTV1	overPTV1	Part of PTV1 that overlaps with larynx for edema+8 mm, superior constrictor m+8 mm, mandible + 8 mm, parotids, masticatory mm, esophagus, mid/low constrictor mm	63	PTV63
	truePTV1	Rest of PTV1	70	PTV70
PTV2	None		63	PTV63
PTV3	overPTV3	Part of PTV3 that overlaps with larynx for edema+8 mm, sup/mid/low constrictor mm+8 mm, parotids+8 mm, masticatory mm+8 mm, esophagus+8 mm	50.75	PTV50.75
	lowPTV3	Part of PTV3 that covers ipsilateral (to neck disease if present) level IV (and level III is negative) and/or contralateral (to neck disease or both heminecks if no neck disease is present) levels III and IV; if disease is present on both sides, each side is treated as ipsilateral one	50.75	PTV50.75
	truePTV3	Rest of PTV3 (or without lowPTV3 and overPTV3)	58.1	PTV58.1

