5.6.2 Dose Specification

5.6.2.1 The prescription dose is the isodose which encompasses at least 95% of the planning target volume (*PTV*). No more than 10% of any planning target volume (*PTV*) will receive >110% of its prescribed dose ($V_{10\%} \leq 110\%$). No more than 1% of any planning target volume (*PTV*) will receive <95% of its prescribed dose ($V_{95\%} > 99\%$). No more than 1% or 1 cc of the tissue outside the PTVs and any OAR (unspecified tissue) will receive >110% of the dose prescribed to PTV1.

5.6.2.1 The prescription dose to the PTV's and subPTV's is reported in table 5. Breaks in treatment should be minimized. Break in treatment time of more than 5 days will be considered a major variation.

5.6.2.2 The reported doses for each PTV shall include the prescription dose as well as the maximum point dose, % target volume receiving > 110% and >115% of its prescribed dose and the % target volume receiving < 95% of the prescribed dose, and the mean dose to the PTV.

5.6.2.3 The dose prescription is to be based on a dose distribution corrected for heterogeneities

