5.6.3 Critical Normal Structures

DVHs must be generated for all critical normal structures and the unspecified tissues. Dose constraints to normal tissues (and PTV's) should be as per table 7.

Table 7.

Group	Region of interest		
1	Cord+4 mm	0.1 cc	Max dose 45 Gy
	Brainstem	0.1 cc	Max dose 54 Gy
	Brain	1 cc	Max dose 60 Gy
	Larynx for edema+8 mm-over2	Portion overlapping with PTV2	Max dose 63 Gy
	Larynx for edema+8 mm	Portion not overlapping with PTV2	Max dose 50.75 Gy
	Mandible+8 mm		Max dose 63 Gy
	Sup constrictor m+8 mm-over2	Portion overlapping with PTV2	Max dose 63 Gy
	Sup constrictor m+8 mm	Portion not overlapping with PTV2	Max dose 50.75 Gy
	Mid constrictor m – over2	Portion overlapping with PTV2	Max dose 63 Gy
	Mid constrict m+8 mm	Portion not overlapping with PTV2	Max dose 50.75 Gy
	Low constrictor m – over2	Portion overlapping with PTV2	Max dose 63 Gy
	Low constrict m+8 mm	Portion not overlapping with PTV2	Max dose 50.75 Gy
	Parotids – over2	Portion overlapping with PTV2	Max dose 63 Gy
	Parotids+8 mm – over3	Portion overlapping with PTV3	Max dose 50.75 Gy
	Masticatory mm – over2	Portion overlapping with PTV2	Max dose 63 Gy
	Masticatory mm+8 mm	Portion not overlapping with PTV2	Max dose 50.75 Gy
	Esophagus – over2	Portion overlapping with PTV2	Max dose 63 Gy
	Esophagus+8 mm – over3	Portion overlapping with PTV3	Max dose 50.75 Gy
Mucosa -1		V66.5 Gy<64.5 cc	
	Unspec. Tissue	1 cc	Max dose 77 Gy
2	overPTV1	Portion overlapping with OAR's (table 5)	V60 Gy >99%
	truePTV1	PTV1-overPTV1	V66.5 Gy >99%
	PTV2		V60 Gy >99%
	overPTV3	Portion overlapping with OAR's (table 5)	V48.2 >99%
	lowPTV3	Low/mid neck PTV3 (table 5)	V48.2 >99%
	truePTV3	PTV3-lowPTV3-overPTV3	V55.2 >99%
3	Mucosa -2	Portion not overlapping with any PTV	Max dose 30 Gy
	Parotids	At least one	V30<50% (whole DVH)

Brachial plexus		Max dose 60 Gy
Inner ears		Mean D <40 Gy
Esophagus-out	Portion outside PTV3+8 mm	Dmax 45 Gy

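### Table 8 scores only a dose floor for the reduced-dose volumes, and its mandible and superior constrictor limits contradict Table 7, so the quality score can mislabel whether de-escalation was delivered

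*Combined protocol and SAP*

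**What the plan says.** **Scoring (5.10, Table 8).** "Each treatment shall be scored with regard to the coverage of each PTV". Targets are scored in four groups, each labelled by its prescription (PTV70 down to PTV50.75). Organs at risk are scored in the same table. The one PTV criterion is V95%: above 99% is per protocol, 95% to 99% is minor, and below 95% is major.

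**The experimental dose (5.5, Table 6).** Three subvolumes carry the reduction: overPTV1 (63 Gy instead of 70 Gy), and overPTV3 and lowPTV3 (50.75 Gy instead of 58.1 Gy). overPTV3 is defined by organ overlap: "Part of PTV3 that overlaps with larynx for edema+8 mm, sup/mid/low constrictor mm+8 mm, parotids+8 mm, masticatory mm+8 mm, esophagus+8 mm". lowPTV3 is defined by neck level, starting with "Part of PTV3 that covers ipsilateral (to neck disease if present) level IV". overPTV1 shares the label PTV63 with PTV2, which is not a reduced volume; overPTV3 and lowPTV3 share PTV50.75.

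**Upper dose (5.6.2).** "No more than 10% of any planning target volume (*PTV*) will receive >110% of its prescribed dose". The next items require reporting of the share of "target volume receiving > 110% and >115% of its prescribed dose", together with the maximum and mean dose. Table 8 uses none of these values.

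**Organ limits (5.6.3, Table 7, against Table 8).**
- Mandible: Table 7 Group 1 sets a 63 Gy maximum on mandible+8 mm. Table 8 gives 70 Gy as per protocol, "Max Dose 73.5Gy" as minor and 75 Gy as major.
- Superior constrictor+8 mm: Table 7 Group 1 sets a maximum of 63 Gy inside PTV2 and 50.75 Gy elsewhere. Table 8 accepts V65 below 70% as per protocol.
- Esophagus: Table 7 sets a maximum of 63 Gy over PTV2 and 50.75 Gy over PTV3, and 45 Gy only for "Portion outside PTV3+8 mm" (the Esophagus-out line of Group 3). Table 8 gives 45/47.3/49.5 Gy and names no portion.

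**The concern.** The trial has one arm, and what it tests is a lower dose to selected parts of the target. A fidelity score for such a trial should show whether the lower dose was given. Table 8 asks only whether each volume received enough. A planner who leaves the reduced volumes at the standard dose gains coverage and loses nothing on the PTV rows.

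One would then look to the organ rows to detect the excess. Two of them are looser than the planning limits that produce the de-escalation, and lowPTV3 is not tied to an organ at all. If the report gives the share of patients treated per protocol, readers will take it as the share who were de-escalated, and Table 8 does not support that.

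**Working it through.** **1. Reproduce the plan's own floors.** Table 7 Group 2 states the V95% criterion in Gy, as 0.95 × prescription:
- 0.95 × 70 = 66.5 (stated 66.5)
- 0.95 × 63 = 59.85 (stated 60)
- 0.95 × 58.1 = 55.2 (stated 55.2)
- 0.95 × 50.75 = 48.2 (stated 48.2)

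The floors in Tables 7 and 8 agree. The difference lies in the ceilings.

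**2. Leave the reduced volumes at the standard dose.** Ratio = standard dose / reduced prescription; 110% ceiling = 1.10 × reduced prescription.

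| Volume | Ratio | 110% ceiling | PTV row in Table 8 | 110% rule |
|---|---|---|---|---|
| overPTV1 | 70/63 = 111.1% | 69.3 Gy | per protocol | broken |
| overPTV3, lowPTV3 | 58.1/50.75 = 114.5% | 55.8 Gy | per protocol | broken |
| overPTV1, 68.25 Gy option (5.6) | 68.25/63 = 108.3% | 69.3 Gy | per protocol | not broken |

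Section 5.6.2.1 wants the prescription isodose to enclose at least 95% of a volume. An overPTV1 planned to 70 Gy would therefore have about 95% of its volume above 69.3 Gy, far more than the 10% allowed. In the last row the 110% rule does not detect the missing reduction.

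**3. Pooling.** Because overPTV1 and PTV2 share the label PTV63, a 110% check on the pooled volume would pass an entirely unreduced overPTV1 whenever it forms no more than 10% of PTV63. The documents do not give that share.

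**4. Do the organ rows catch it?**
- lowPTV3 at 58.1 Gy: no organ row is linked to it. The brachial plexus row allows 60 Gy.
- Mandible: 70 − 63 = 7 Gy looser than Table 7, which equals the full PTV1 reduction (70 − 63).
- Superior constrictor: a 63 Gy maximum, read literally, leaves no volume above 65 Gy; Table 8 accepts anything below 70%.
- Middle and lower constrictors and masticatory muscles: ceilings in Table 7, no row in Table 8.
- Larynx (V50 below 30%), parotids (V30 below 50%), esophagus and the four superior constrictor rows act as partial, indirect ceilings.

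The constrictor rows show how partial. With V65, V60, V50 and V40 at 70%, 80%, 90% and 95%, the highest possible mean is 0.70 × Dmax + 0.10 × 65 + 0.10 × 60 + 0.05 × 50 + 0.05 × 40 = 0.70 × Dmax + 17. That is 66.0 Gy at Dmax 70 and 70.9 Gy at Dmax 77. Table 5 gives a mean of 67.3 Gy with a gain of 3.7 Gy, so the reference plan averages 67.3 or 71.0 Gy, depending on which plan the column describes. Meeting the rows then needs Dmax of at least (67.3 − 17)/0.70 = 71.9 Gy or (71.0 − 17)/0.70 = 77.1 Gy. An unreduced plan may pass in some patients and fail in others.

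**5. Esophagus, two readings.** Read as the whole organ, the row scores the 50.75 Gy that Table 7 permits in the PTV3 overlap beyond the 49.5 Gy major value. The 48.2 Gy coverage floor of overPTV3 already exceeds the 47.3 Gy minor value. Read as Esophagus-out, both tables say 45 Gy and there is no conflict.

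**6. Rows that agree.** The per-protocol limits for cord+4 mm, brainstem, brain, brachial plexus and inner ears match Table 7.

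**The case against.** **The dose reduction is controlled elsewhere.** Table 6 prescribes it, the Group 1 ceilings of Table 7 rank above target coverage in 5.6.4, and 5.6.2.1 caps the excess. This stands: an unreduced plan with PTV1 at 70 Gy breaks the dose specification. But Table 8 is where a deviation gets its label, and it leaves this one out.

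**Nothing depends on the score, and the dose is known anyway.** Section 10.3 reports the primary endpoints for all patients and uses no per-protocol set. Section 5.10 exports DVHs for every target and organ, and 5.6.2.2 requires high-dose shares and means. This also stands. A reader might infer that a missed toxicity target could never be traced to undelivered de-escalation; the documents do not support that, because delivered dose can be recovered. What is missing is a rule to summarise it.

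**A plan with no de-escalation would fail other rows.** A reader might infer that such a plan is sure to score per protocol throughout. The documents show this only for the PTV rows; the full score depends on anatomy, as the constrictor bound shows.

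**Table 7 maxima are planning objectives, so looser scoring tolerances can coexist with them.** There is something in this: 5.6.2.1 tolerates hot spots, and Table 5's superior constrictor mean for the proposed plan (63.6 or 67.3 Gy) already exceeds the 63 Gy maximum. A literal V65 of zero should not be pressed. Yet Table 8 matches Table 7 exactly on five other organ limits, and nothing explains why mandible and superior constrictor differ.

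**The esophagus row means Esophagus-out.** This is plausible: it sits among three other rows that carry Group 3 limits. A reader might infer that compliant plans are bound to be scored beyond major; that needs the whole-organ reading, which the text does not settle.

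**Conclusion.** The point holds in limited form. Table 8 gives a per-protocol PTV score to reduced-dose volumes left at 111.1% or 114.5% of prescription, although both breach 5.6.2.1, and no organ row is tied to lowPTV3. Its mandible and superior constrictor rows contradict Table 7 Group 1. The esophagus row is ambiguous; it conflicts with Table 7 on one reading and not on the other.

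A fully per-protocol score without de-escalation is possible but not assured. The harm is a misleading record of treatment fidelity in a single-arm trial, not a wrong estimate of toxicity or control. It should be fixed, but it does not invalidate the primary analysis.

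This rests on two assumptions: that the 110% rule applies to each subvolume against its own Table 6 prescription, and that an unreduced volume is covered as 5.6.2.1 asks at the standard dose.

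**What to change.** 1. Add a row to Table 8 that scores the existing 110% rule of 5.6.2.1, using the percentages that 5.6.2.2 already requires.
2. Score overPTV1 separately from PTV2. State that under the 68.25 Gy option an unreduced overPTV1 (108.3%) passes the 110% row, so that case needs its own check of delivered against prescribed dose.
3. Reconcile the mandible, superior constrictor and esophagus rows with Table 7, naming the organ portion in each. Which limit stands is for the sponsor to decide.
4. Report beside the primary endpoints the proportion of patients in whom the reduced dose was delivered, by a definition fixed in advance.

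The cost is protocol wording and rescoring of DVHs that 5.10 already exports. No new data or procedure is needed. The downside is that some plans will change score.

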5.11 Radiation Therapy Toxicity Adjustments

5.11.1 Treatment Interruptions

Interruptions in radiotherapy are strongly discouraged based on the well known correlation between overall treatment time and outcome especially in the context of IMRT alone.

5.12 Toxicity Reporting Guidelines

5.12.1 For both acute and late effect, the NCI CTCAE Version 4.0 will be used (Appendix 1). All events will be recorded and loaded into software that is routinely used for clinical purposes in our Department called Mosaiq (v1.6 IMPAC, Sunnyvale, California).

5.12.2 The Head and Neck Cancer specific module of the MD Anderson Symptom Index (MDASI-HN)(Appendix 2) and the Xerostomia questionnaire (Appendix 3) will be used as patient-reported outcome instruments^{48,49}

5.12.3 The swallowing related instruments (see 1.6) are: Penetration/Aspiration scale (Appendix 4); Montreal Cognitive Assessment (Appendix 5); MD Anderson Dysphagia Inventory (MDADI)(Appendix 6).

5.12.4 All life-threatening (*grade 4*) toxicities from protocol treatment will be reported to the PI within 24 hours of discovery. **Institutional guidelines will be followed in reporting serious adverse events to the IRB.**

6 DRUG THERAPY

Chemotherapy will be reserved for patients with T3 lesions (3.1.1) and/or clinically staged nodal disease greater than N1 and/or evidence of microscopic extracapsular extension after neck surgery (T3 and/or N2a \geq 5cm, N2b, N2c, N3 stage cancer or Nx with ECE). Chemotherapy consists of single agent cisplatin or carboplatin.

6.1 Cisplatin

6.1.1 The first dose of cisplatin, 40mg/m² IV, will be administered within the first 3 days of the start of RT and repeated weekly for the first 3 weeks and last 3 weeks of RT. Patients will not receive chemotherapy during week 4 of treatment. The last dose of chemotherapy may be given up to one week following completion of RT. If RT is held, cisplatin will also be held.

6.1.2 Hydration: Patients should be adequately hydrated with 1-2 liters of fluid PO in the 24 hours prior to and post cisplatin administration.

6.1.3 Immediately prior to the cisplatin administration, patients should receive 1 Liter of Normal Saline over 1-2 hours.

6.1.4 Cisplatin 40 mg/m² should be mixed in 1 liter normal saline and infused over 2-3 hours. Cisplatin is a commercially available agent.

6.1.5 *Antiemetics:* Antiemetics must be given in conjunction with cisplatin. Antiemetic selection will be at the discretion of the treating physician and is recommended with each chemotherapy infusion. These include dolasetron, ondansetron, dexamethasone, lorazepam, or prochlorperazine. Therapy for prevention of delayed emesis may be considered.

6.2 Cisplatin Dose Modification for toxicity

6.2.1 *Hematologic:* Patients must have an ANC ≥ 1000 /mm³ and platelets $>100,000$ / mm³ prior to receiving cisplatin. If the patient's counts are below these levels, cisplatin will not be given and weekly dosing reinstated the following week as long as counts are within acceptable treatment parameters. Held doses will not be made up. Grade 4 neutropenia (ANC <500 /mm³) or febrile neutropenia requiring hospitalization for antibiotics or grade 4 thrombocytopenia (platelets $<25,000$ / mm³) require a dose reduction of cisplatin of 25%.

6.2.2 *Neurotoxicity:* Patients developing grade 2 sensory or motor neuropathy or $>$ grade 2 hearing loss will have cisplatin discontinued and carboplatin substituted (see 6.3.4).

6.2.3 *Nephrotoxicity:* Measurement of serum creatinine is required before each treatment with cisplatin and must be within normal limits. Serum creatinine above the upper limit of normal necessitates creatinine clearance assessment using the modified Cockcroft-Gault formula. If the patient's calculated creatinine clearance is less than 60 ml/min, cisplatin will be held and additional hydration will be given. Serum creatinine and creatinine clearance should be repeated weekly and/or as needed after additional hydration is given. Cisplatin may be reinstated, under the discretion of the treating physician, if the CCl improves to greater than or equal to 60 ml/min. If the creatinine clearance does not improve despite additional hydration, cisplatin will be substituted with carboplatin (see section 6.3.4). Held doses will not be made up.

6.2.4 *Switch to Carboplatin:* In case of any of the followings, cisplatin will be substituted to carboplatin: creatinine clearance < 60 ml/min; ototoxicity; peripheral sensory or motor neuropathy grade 2. Weekly carboplatin dosing would be at AUC=2. Dose modifications of cisplatin and carboplatin will be under the discretion of the treating medical oncologist. If the patient has peripheral neuropathy $>$ grade 1, and/or frequency hearing loss that interferes with activities of daily living, cisplatin can be dose reduced or substituted with carboplatin.

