3.2 Ineligibility Criteria

- 3.2.1 Evidence of distant metastases.
- 3.2.2 Absence of macroscopic disease after upfront surgery, i.e. TxNx and TxN0. TxN+ and T1-3Nx are eligible if the T/N stage categories meet the criteria of 3.1.1
- 3.2.3 Previous irradiation for head and neck tumor; concurrent chemotherapy other than the treatment per protocol; previous chemotherapy \leq 3 months from start of RT.
- 3.2.4 Active untreated infection.
- 3.2.5 Major medical or psychiatric illness, which in the investigators' opinion would interfere with either completion of therapy and follow-up or with full and complete understanding of the risks and potential complications of the therapy.
- 3.2.6 Use of amifostine or pilocarpine before and during radiotherapy is not allowed.
- 3.2.7 Serum creatinine >1.3 or ULN, CCL < 60 cc/min, Peripheral neuropathy > grade 1, and/or frequency hearing loss that interferes with activities of daily living are contraindications to cisplatin but not to carboplatin (6.2.4).
- 3.2.8 Patients with > 10 pack years of smoking history and/or currently a smoker at the time of treatment.

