6.3 Carboplatin

6.3.1 Carboplatin may be administered as a substitution for cisplatin when cisplatin-related toxicities occur as described in 6.3 Cisplatin Dose Modification for Toxicity or when patients present with $>$ grade 2 sensory or motor neuropathy, $>$ grade 2 hearing loss, or <60 ml/min calculated creatinine clearance at baseline.

6.3.2 The first dose of carboplatin, AUC=2 IV, will be administered within the first 3 days of the start of RT and repeated weekly during the 7 weeks of RT. The last dose of chemotherapy may be given up to one week following completion of RT. If RT is held, carboplatin will also be held.

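### Sections 3.2.7, 6.2.2, 6.2.4 and 6.3.1 give inconsistent rules on cisplatin for neuropathy and hearing loss: mandatory replacement in some sentences, optional dose reduction in another

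*Combined protocol and SAP*

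**What the plan says.** Four sections of the protocol govern cisplatin in patients with neuropathy or hearing loss.

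- **6.2.2 (Neurotoxicity).** The neuropathy trigger is "Patients developing grade 2 sensory or motor neuropathy". The hearing trigger, as printed, is loss above grade 2. In either case the patient "will have cisplatin discontinued and carboplatin substituted".
- **6.2.4 (Switch to Carboplatin), first sentence.** The rule is again mandatory: "cisplatin will be substituted to carboplatin: creatinine clearance < 60 ml/min; ototoxicity; peripheral sensory or motor neuropathy grade 2". No grade is attached to ototoxicity.
- **6.2.4, discretion sentence.** "Dose modifications of cisplatin and carboplatin will be under the discretion of the treating medical oncologist".
- **6.2.4, last sentence.** For neuropathy above grade 1, and/or hearing loss that interferes with daily activities, "cisplatin can be dose reduced or substituted with carboplatin".
- **3.2.7 (Ineligibility Criteria).** "Peripheral neuropathy > grade 1" and/or hearing loss that interferes with daily activities is a contraindication to cisplatin but not to carboplatin. The section refers the reader to 6.2.4.
- **6.3.1 (Carboplatin).** Carboplatin may be given in place of cisplatin when cisplatin toxicity occurs, "or when patients present with" neuropathy or hearing loss above grade 2 (as printed) at baseline.

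**The concern.** A rule for stopping a drug should lead two clinicians with the same patient to the same action, or say openly that the choice is theirs. Here the action depends on which sentence is read. Two sentences require cisplatin to be replaced, and a third allows it to continue at a reduced dose.

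The choice affects more than the drug name. Section 6.1.1 gives cisplatin in the first three and last three weeks of radiotherapy with none in week 4, whereas 6.3.2 gives carboplatin weekly through the seven weeks. Platinum exposure could therefore differ between patients with the same toxicity because of wording alone. That is first a patient-safety matter. It also bears on interpretation, because hearing impairment and tinnitus are among the Appendix 1 items graded to 3 or above, and grade 3+ toxicity is a primary endpoint.

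**Working it through.** No arithmetic applies. The check applies each rule, as printed, to the same patient.

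**Case 1: grade 2 neuropathy developing on treatment.**
- 6.2.2: cisplatin is stopped and carboplatin substituted.
- 6.2.4, first sentence: carboplatin is substituted.
- 6.2.4, last sentence: grade 2 is above grade 1, so either reduced-dose cisplatin or carboplatin is allowed.

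Two sentences mandate replacement and one makes it optional.

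**Case 2: grade 2 neuropathy at entry.**
- 3.2.7: cisplatin is contraindicated and carboplatin is not; see 6.2.4.
- 6.2.4, last sentence: reduced-dose cisplatin or carboplatin.
- 6.3.1: the printed baseline threshold (above grade 2) is not reached.

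3.2.7 and the section it cites disagree on whether cisplatin can be used at all. The baseline grades in 3.2.7 and 6.3.1 differ as printed.

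**Case 3: grade 2 hearing loss on treatment.** In Appendix 1, for adults outside a monitoring program, grade 2 already includes limitation of instrumental daily activities. I assume that this counts as interference in the sense of 6.2.4.
- 6.2.2: the printed trigger (above grade 2) is not met, so no switch is required.
- 6.2.4, first sentence: ototoxicity is present, so the switch is mandatory.
- 6.2.4, last sentence: reduction or substitution is optional.

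The three sentences give three different answers.

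**Case 4: the same hearing loss at entry.**
- 3.2.7: cisplatin is contraindicated and carboplatin is not.
- 6.2.4, last sentence: reduced-dose cisplatin or carboplatin.
- 6.3.1: the printed threshold is not reached.

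**Does the result depend on symbols lost in text extraction?** It might in part. Section 3.1.5 prints strict inequalities for prostate cancer stage, Gleason score and disease-free years where the schema prints inclusive ones. On the other hand, inclusive signs do survive in 6.2.1. Reading every above-grade-2 sign in 6.2.2 and 6.3.1 as grade 2 or higher gives the following:
- Case 1 does not change. The 6.2.2 neuropathy trigger carries no sign, and grade 2 falls under the last sentence of 6.2.4 on either reading.
- Case 2: 6.3.1 then agrees with 3.2.7 on the neuropathy grade. The conflict between 3.2.7 and 6.2.4 remains.
- Case 3: the no-switch answer disappears at grade 2. Mandatory against optional remains. Ototoxicity of grade 1 would still be a mandatory switch under 6.2.4 and no switch under 6.2.2.
- Case 4: 6.3.1 is then met. The conflict between 3.2.7 and 6.2.4 remains.

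**Cross-references.** They do not settle the matter. Sections 6.2.2 and 6.2.3 send the reader to a 6.3.4 that does not appear in the text. Section 6.3.1 cites 6.3 for cisplatin dose modification, which is in 6.2.

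**The case against.** **The discretion sentence reconciles the paragraph.** On this view 6.2.4 states a default, then gives the oncologist discretion, then lists the options. This is the best reading in the plan's favour, and the sentence must be weighed. But it speaks of dose modifications and does not say that it displaces the mandatory wording in 6.2.2 and at the head of 6.2.4. It also does not touch the contraindication in 3.2.7.

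**The clauses cover different situations.** 6.2.2 concerns patients who develop neuropathy. The last sentence of 6.2.4 speaks of a patient who has it, and its wording echoes 3.2.7. A split between baseline and on-treatment rules is plausible, but the text does not state it, and the sentence sits under the heading for dose modification for toxicity. Even if granted, 6.2.4 would allow reduced-dose cisplatin at entry for a condition that 3.2.7 calls a contraindication to cisplatin.

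**The divergence is narrow.** For grade 2 neuropathy, carboplatin is compatible with 3.2.7, 6.2.2 and both statements in 6.2.4. The open question is only whether reduced-dose cisplatin is also available. That is right, and it limits the point.

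**Stronger readings that the documents do not support.**
- A reader might infer that a grade 2 patient at entry is barred from cisplatin and has no route to carboplatin. That is not so. 3.2.7 says the condition does not contraindicate carboplatin, 6.2.4 offers it, and 6.3.1 is permissive and excludes no one.
- A reader might treat the baseline grade mismatch between 3.2.7 and 6.3.1 as established. It may be an extraction artefact.
- A reader might link the neuropathy rules to the primary endpoint through the neuralgia item in Appendix 1. Neuralgia there is a pain item, and Appendix 1 has no item for peripheral sensory or motor neuropathy.

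**Conclusion.** The rules are inconsistent as written. The firm core is twofold. First, mandatory replacement (6.2.2 and the first sentence of 6.2.4) stands against optional reduction or replacement (last sentence of 6.2.4) for grade 2 neuropathy. Second, 3.2.7 calls the same condition a contraindication to cisplatin while pointing to a section that allows cisplatin at a reduced dose. Neither part depends on a symbol that extraction could have altered.

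The hearing-loss triggers also disagree. The no-switch answer in Case 3 depends on the printed sign, and the third answer depends on the assumption about instrumental daily activities. The baseline grade difference in 6.3.1 is a possible, not a proven, inconsistency.

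The size cannot be given as a number. The rules apply only to patients who receive chemotherapy under section 6, and the documents do not say how many of them would develop or present with these conditions. Any shift in the late grade 3+ rate is therefore unquantified. The planned 60 patients, the 50 used for precision, and the stopping table are unaffected. The case for acting is that a safety rule should not contradict itself.

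**What to change.** The sponsor should reconcile 3.2.7, 6.2.2, 6.2.4 and 6.3.1 as follows:

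1. For neuropathy and for hearing loss separately, state one threshold and one action at baseline, and one threshold and one action during treatment. Give a grade for ototoxicity, and print the inequality signs unambiguously.
2. Say whether the last sentence of 6.2.4 applies at baseline, during treatment or both, and make it agree with 3.2.7.
3. Say whether the oncologist's discretion operates within the mandatory rules or overrides them.
4. Correct the references to 6.3.4 in 6.2.2 and 6.2.3, and the reference to 6.3 in 6.3.1.

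The clinical content is for the sponsor to decide; no view is taken here on which threshold or action is right. The cost is a wording amendment, with no change to sample size, endpoints or analysis.
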